6.3.2 Amino Acid Infusion: Renal Protection

It has been shown that the renal absorbed dose, which is the treatment-limiting factor of PRRT, can be effectively reduced by the concomitant administration of cationic amino acids. Based on the joint IAEA, EANM and SNMMI practical guidance on PRRT in NETs [35] a solution of 25 g lysine and 25 g arginine in 2 L saline is recommended to be infused concomitant to the PRRT administration over 4 hours, starting 30 to 60 minutes before the infusion of ¹⁷⁷Lu-OPS201. The infusion time can be extended to 6 hours in case of e.g. technical infusion problems, interruption of infusion due to AEs or subjects' intolerance of the high-volume load in a short time. The guidelines for the infusion of the amino acids should be followed as closely as possible, unless there is a contraindication. If the infusion is not complete after 4 hours, a long infusion line (2 m) can be used to continue the infusion while the whole-body scan and SPECT/CT scan are done (but note the long line can cause increased pressure and result in a slowing of the infusion rate which might require correction). The line should be made of PVC (Non-DEHP and free of Latex). The infusion of OPS201 must be complete when the long infusion line is inserted as the extra length of line would increase the amount of radioactive substance in the infusion line and so increase the radiation exposure to the public and to staff.

Centres experienced in PRRT treatment can use their established amino acid solution, if it is covered by the recommendations of the joint IAEA, EANM and SNMMI practical guidance on PRRT in NETs and agreed with the sponsor, or Ipsen amino acid solution (auxiliary medicinal product OPS301, depending on the availability at the study site). The exact formulation and source must be documented in the eCRF. OPS301 has been formulated in compliance with the established guidelines and like other similar products is acidic (pH5.5).

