Descriptive summaries of following ECG and Holter parameters will be calculated: heart rate, RR interval, PR interval, QRS interval, QT interval, QTcB, and QTcF. The number and percentage of subjects with normal, abnormal (not clinically significant), abnormal (clinically significant) findings will be presented.

For laboratory data, abnormal values will be flagged in the data listings and a list of clinically significant abnormal values will be presented.

Haematological and biochemical toxicities will be recorded and graded according to the NCI CTCAE. The NCI CTCAE Grade 3 and 4 haematology and biochemistry parameters by subject and by cycle will be tabulated and listed. For white blood cells, neutrophils, platelets and haemoglobin, with associated Grade 3 or 4 toxicities, nadir and day to nadir will be calculated.

Also, descriptive summaries will be performed for the efficacy data, the data from the quality of life questionnaire, the dosimetry data, the bone marrow safety data and the renal toxicity data for each time point as applicable.

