1.3.3.3.2 Blood Biochemistry

Biochemistry parameters include sodium, potassium, chloride, calcium, glucose, creatinine, urea, albumin, total bilirubin, AST, ALT, alkaline phosphatase, GGT, C-reactive protein. Creatinine clearance will also be calculated.

The eGFR value will be calculated by the Modification of Diet in Renal Disease (MDRD) formula.

Biochemistry will be measured at the Screening Visit, at Visits 1 to 3 and optional Visits 4 and 5 (predosing, 24±1 hour (Day 2), 48±1 hour (Day 3), 72 to 96 hours (Day 4 to 5), 144 to 168 hours (Day 7 to 8) and Day 15±2 days), Follow-up Visits, the EOCT/EOAC/EW Visit and the visits in the 2-year long-term follow-up period.

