3.1.7 Exploratory endpoint(s)

3.1.7.1 Exploratory Efficacy Endpoints

CCI

CCI

3.1.7.2 *Exploratory Biomarkers*

CCI

3.1.8 *Multiplicity*

No multiple testing will be performed in this study.

3.1.9 *Significance testing and estimation*

As this is a descriptive safety and tolerability/efficacy study, no formal statistical testing will be carried out. If p-values are provided, they will only be provided for exploratory purposes only.

3.2 **Analysis methods**

3.2.1 *Safety*

All safety data will be included in the data listings and summary tables will be based on the Safety Analysis Set. Summary tables will be presented by study Part, cohort (part B only), overall Part B and overall.

3.2.1.1 *Dose Limiting Toxicity*

DLTs (see section 3.2.18) will be listed by study Part, cohort (part B only), radioactivity level adapted or not (part B only) and subject. Listings of AEs and abnormal laboratory values defined as DLTs will be also provided sorted by study Part, cohort (part B only), radioactivity level adapted or not (part B only) and subject.

A summary of DLTs will be provided, presenting the number of subjects with DLTs, the number of DLTs and the number of DTLs per type of DLTs (presented by decreasing frequency), by study Part, cohort (part B only), radioactivity level adapted or not (part B only) and overall.

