All AEs and SAEs occurring during the Screening period and more than 6 months after the last dose of study medication will be listed and flagged as occurring before or after (during period 3) the active phase of the study; however, these will not be defined as TEAEs.

TEAEs will be summarised by study part, cohort (part B only) and overall with the number and percentage of subjects with adverse events classified by primary system organ class and preferred term. The number of occurrences of a TEAE will also be presented. The summary of AEs will also be repeated by time period. A listing of AEs by time period will also be presented.

In addition, summary tables will also be presented for SAEs, TEAEs related to ¹⁷⁷Lu-OPS201, TEAEs related to OPS301, treatment emergent ¹⁷⁷Lu-OPS201 related SAEs, OPS301 related SAEs, TEAEs leading to premature discontinuation of study medication, TEAEs leading to dose delays, TEAEs leading to dose reduction, TEAEs leading to dose interruption, TEAEs per decreasing frequency, TEAEs by associated NCI CTC worst grade and by causality. There will also be a separate summary for Adverse Events of Special Interest (AESI) which will be defined as any TEAE related to ¹⁷⁷Lu-OPS201 which occurs the day of ¹⁷⁷Lu-OPS201 administration (same date as ¹⁷⁷Lu-OPS201 administration and at any cycle).

Summary tables of adverse events will be provided with the number and percentage of subjects with adverse events classified by primary system organ class, preferred term (ordered alphabetically) and associated CTCAE version 5.0 worst grade. In the event of multiple occurrences of the same adverse events being reported by the same subject, the maximum intensity (Grade 5 > Grade 4 > Grade 3 > Grade 2 > Grade 1 > missing > not applicable) and the most serious causality (related > not related) will be chosen.

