3.2.1.3 Laboratory data

A separate listing of normal ranges for SI and local laboratories units will be provided by study site laboratory, gender and age where relevant.

Laboratory data (including hematology, biochemistry, pituitary markers and urinalysis) will be listed in SI and local laboratories units and abnormal values will be flagged (High, [H], Low [L], clinically significant [C], CTCAE version 5.0 grade (G)) where applicable. Any unscheduled laboratory assessments will be flagged [U] in the listings. In addition, a listing of clinically significant abnormal values will be presented.

As multiple local laboratories are used within the study, a data normalisation method (refer to [Appendix 1: Derived Data](#), and Ref. 5, 6, 7) will be used before summarising the data. The normalized lab data values will be also included in the lab data listings together with the reference normal range limits used for the normalisation.

(a) Hematology, Biochemistry and Pituitary Markers

For hematology, biochemistry and pituitary marker parameters, the baseline will be defined as the last measurement collected prior to the first dose of study drug.

For hematology, biochemistry and pituitary marker parameters, summary statistics, by study part, cohort (part B only) and overall, will be presented at each scheduled assessment for normalised actual values and changes from baseline. For pituitary markers, all values will be displayed in a listing, however the summary tables may exclude any results if it was drawn while the subject was receiving medication that may have been deemed to impact the result.

The determination of the medications impacting the result will be based upon medical monitor review and reflected in a footnote.

Shift tables from Baseline to worst post-baseline and also, each post baseline visit. In the shift tables, the number and percentages of subjects with low, normal, or high values will be presented by study part, cohort (part B only) and overall.

For hematology and biochemistry, summary statistics by study part, cohort (part B only) and overall, will be also provided for nadir and day to nadir by cycle (time from cycle baseline to nadir during the same cycle) and on lab toxicities after start of study medication with worst CTCAE version 5.0 Grades 3 and 4 (refer to Appendix 1, Derived data).

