(18) **A nadir** for a subject is defined as the lowest laboratory value during the whole treatment period (all cycles combined) among all infusions for that subject and a nadir for a cycle is defined as the lowest laboratory value in that cycle. The day to nadir in a cycle is the number of days between the nadir and the first date of study medication intake of that cycle.

(19) **Whole body absorbed dose**

$$\text{AbsorbedDose_WholeBody [Gy]} = \text{AUC}_{\text{WholeBody}} [\text{Bq.s}] \times E_{\text{beta}} / \text{Weight}_{\text{WholeBody}} [\text{kg}]$$

With $E_{\text{beta}} = 2.3664 \times 10^{-14} \text{ J.Bq}^{-1} \cdot \text{s}^{-1}$.

(20) Whole body specific absorbed dose

$$\text{Specific_AbsorbedDose_WholeBody [Gy/GBq]} = \frac{\text{AbsorbedDose_WholeBody [Gy]}}{\text{Radioactivity_administered [GBq]}}$$

(21) Amount excreted (Ae) for cold PK urine sample

$$\text{Ae [ng]} = \text{ConcentrationOPS201_urine (ng/mL)} \times \text{volume urine collected (mL)}$$

CCI

CCI

CCI

CCI

CCI

CCI

CCI

CCI

CCI

CCI

CCI

CCI

CCI

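### The SAP extends nadir tables to all biochemistry, so creatinine, urea and the liver tests are summarised at their most favourable value

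*SAP*

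**What the plan says.** **Nadir.** Protocol 11.4.10 confines the analysis to four blood-count parameters and ties it to severe toxicity: "For white blood cells, neutrophils, platelets and haemoglobin, with associated Grade 3 or 4 toxicities, nadir and day to nadir will be calculated". SAP 3.2.1.3 widens it: "For hematology and biochemistry, summary statistics by study part, cohort (part B only) and overall, will be also provided for nadir and day to nadir". The summary is made separately for each cycle. SAP Appendix 1, item 18 supplies the rule: "a nadir for a cycle is defined as the lowest laboratory value in that cycle". The subject-level nadir is likewise the lowest value over the whole treatment period. Neither place gives a direction by parameter. SAP 1.3.3.3.2 lists the panel: "Biochemistry parameters include sodium, potassium, chloride, calcium, glucose, creatinine, urea, albumin, total bilirubin, AST, ALT, alkaline phosphatase, GGT, C-reactive protein"; eGFR is calculated as well. SAP section 5 (changes from protocol) mentions one dosimetry endpoint and the definition of events of special interest, but not this extension.

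**Other biochemistry outputs.** The sentence in 3.2.1.3 that orders the nadir also orders summaries of worst Grade 3 and 4 laboratory toxicity. The same section plans "Shift tables from Baseline to worst post-baseline and also, each post baseline visit", categorised as low, normal or high. It also plans listings of biochemical toxicities and of low eGFR, and individual plots over time of creatinine, eGFR, AST, ALT, alkaline phosphatase and bilirubin.

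**OPS301.** SAP 3.2.1.2 plans tables of "TEAEs related to OPS301" and of OPS301-related serious events. For safety in general, SAP 3.2.1 says "summary tables will be based on the Safety Analysis Set", which SAP 2.2 defines as everyone who received study medication. Protocol 6.3.2 offers OPS301 as an alternative to a centre's own amino acid solution: "auxiliary medicinal product OPS301, depending on the availability at the study site". Protocol 8.1.2.2 has causality to OPS301 recorded for its recipients.

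**The concern.** A nadir is the harmful extreme for blood counts, eGFR and albumin. For creatinine, urea, bilirubin and the liver enzymes the harmful extreme is the peak. Applying one lowest-value rule to the whole panel places a subject's worst eGFR and best creatinine under the same heading.

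Safety is the primary objective, the kidney is a dose-limiting organ, and liver tests are among the criteria for withdrawal from treatment (Protocol 6.4). A per-cycle summary of the extreme value and its timing is a natural place to look for renal or hepatic effects. As specified, it would answer the opposite question for those analytes.

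The OPS301 matter is smaller. If the default analysis set supplies the denominator, subjects who never received the product, and so cannot contribute a related event, would lower the reported percentage. Cohort differences could then partly reflect site supply.

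**Working it through.** The plan states no figure on this point, so there is nothing to reproduce. The check compares the texts, applies the SAP rule to assumed profiles, and shows the OPS301 arithmetic over a range.

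**1. Scope and direction**

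| | Protocol 11.4.10 | SAP 3.2.1.3 with Appendix 1, item 18 |
|---|---|---|
| Parameters | White cells, neutrophils, platelets, haemoglobin | All haematology and all biochemistry |
| Condition | Grade 3 or 4 toxicity | None in the nadir definition |
| Rule | Nadir | Lowest value, whatever the parameter |

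SAP 1.3.3.3.2 names 14 analytes. For seven of them (creatinine, urea, total bilirubin, AST, ALT, alkaline phosphatase, GGT) the toxicity of interest is a rise. For albumin the minimum is the relevant extreme; for sodium, potassium, chloride and calcium either extreme can be.

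**2. The rule applied to one cycle**

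The profiles are assumed, in multiples of the upper limit of normal. Times are days after dosing and follow the Part B visit schedule (0, 1, 2, 3, 6, 14, 28, 41). The SAP statistic is the minimum over the cycle; the toxicity-directed statistic is the maximum.

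- Creatinine 0.8, 0.8, 0.9, 1.0, 1.3, 1.9, 2.6, 3.2: SAP nadir 0.8 at day 0; peak 3.2 at day 41.
- ALT 0.9, 1.0, 1.4, 2.5, 5.6, 3.0, 1.2, 0.7: SAP nadir 0.7 at day 41; peak 5.6 at day 6.

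A steadily rising value therefore returns the cycle's own starting value at day 0. A transient peak returns a value from outside the episode.

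**3. Whether another summary supplies the peak**

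- Worst Grade 3 and 4 summaries capture severe events but give neither the value nor its day.
- Shifts to worst post-baseline show that a value went high, not by how much.
- By-visit statistics include a maximum (SAP 3.2.15), but across subjects at one visit rather than within a subject over a cycle.
- Listings and plots show individual values but do not summarise them.

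The toxicity can be seen in the report. The per-cycle peak and day to peak are not summarised.

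**4. OPS301 denominator**

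Let N be the treated subjects, k the OPS301 recipients and x the recipients with a related event. The rate among recipients is x/k and among all treated x/N, so the second is k/N times the first. N = 55 is the planned maximum (SAP 1.3.7). The documents do not give k, and x is assumed.

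| k | x | x/k | x/55 | k/55 |
|---|---|---|---|---|
| 14 | 7 | 50.0% | 12.7% | 0.25 |
| 28 | 14 | 50.0% | 25.5% | 0.51 |
| 41 | 20 | 48.8% | 36.4% | 0.75 |
| 55 | 28 | 50.9% | 50.9% | 1.00 |

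**The case against.** The strongest reply is that the table does what its label says: it is called a nadir, it is defined as the lowest value, and the SAP nowhere presents it as a worst-value table. Protocol section 11 also allows the SAP to modify protocol plans. Both points stand, so this is an uninformative and undeclared extension rather than a miscalculation.

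A reader might go further and infer that renal and hepatic toxicity is hidden. The documents do not support that. The worst-grade summary is ordered in the same sentence as the nadir, and the shift tables, toxicity listings and plots cover biochemistry as well. SAP 3.2.1.3 does restrict the baseline-to-worst-grade shift tables to haemoglobin, neutrophils and platelets. Given the other outputs, adding creatinine or bilirubin there is a matter of presentation.

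Nor is the rule wrong for every analyte: the minimum is right for albumin and eGFR and can matter for electrolytes.

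On OPS301, a reader might infer that the planned percentages are definitely diluted. No passage states the denominator of those tables. SAP 3.2.15 uses non-missing observations and allows a clarifying footnote, so a recipients-only denominator is compatible with the text. The output list is redacted, so table populations cannot be checked. The documents do not establish that some subjects will go without OPS301, and SAP 3.2.1.7 counts the recipients, so an overall rate could be recalculated. What stands is that the default analysis set is all treated subjects and nothing names an exception.

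**Conclusion.** The nadir point holds on explicit text. For seven of the 14 listed analytes the SAP would tabulate the most favourable value and its day, under an extension beyond the protocol that section 5 does not declare. The consequence is limited: those rows are uninformative, and the per-cycle peak is missing from the summaries, while the toxicity itself remains visible elsewhere. The numerical profiles are illustrations and do not estimate a bias. The conclusion rests only on the stated definition and on a rise being the harmful direction for those seven analytes.

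The OPS301 point is a secondary request for clarification. The denominator is unspecified and by default would be the Safety Analysis Set. Any understatement is the factor k/N, with k unknown, and vanishes if every subject receives OPS301.

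**What to change.** 1. In SAP 3.2.1.3 and Appendix 1, item 18, either
   - restrict nadir and day to nadir to the protocol's four haematology parameters, or
   - define the per-cycle and overall worst value by direction of toxicity: maximum and day to maximum for creatinine, urea, total bilirubin, AST, ALT, alkaline phosphatase and GGT; minimum and day to minimum for blood counts, eGFR and albumin; both extremes for electrolytes. Glucose and C-reactive protein then need a stated direction too.

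   The second option is more useful because it supplies the missing peak summary.
2. If nadir, or a worst value replacing it, goes beyond the protocol's four parameters, record that in SAP section 5.
3. State in SAP 3.2.1.2 that percentages in the OPS301-related event tables use subjects who received at least one OPS301 infusion, and show that number in each column.

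The cost is SAP wording and programming. No new data are needed: the laboratory values are already collected and the recipients already counted under SAP 3.2.1.7.

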3.2.2 Radiopharmaceutics and Dosimetry

All data will be included in the individual data listings and summary tables will be based on the PP-DAS, Radiopharmaceutical Pharmacokinetic Set or ITT-DAS Set depending of the parameter. Summary tables will be presented by study part, cohort (part B only), overall part B and overall.

(a) Biodistribution and Radioactive Pharmacokinetics

- Maximal uptake (unit: %) in lesions.

Maximal uptake (unit: %) in lesions will be listed by study part, cohort (part B only), radioactivity level adapted or not (part B only), subject, cycle and lesion number. Descriptive statistics, including geometric mean and geometric Coefficient of Variation (CV), will be presented by study part, cohort (part B only) and cycle on the PP-DAS.

Uptake (unit: %) in lesions at each assessment time point will be also displayed, it will be listed by study part, cohort (part B only), radioactivity level adapted or not (part B only), subject, cycle, lesion number and time point.

- Maximal uptake (unit: %) in discernible organs.

Maximal uptake (unit: %) in discernible organs will be listed by study part, cohort (part B only), radioactivity level adapted or not (part B only), subject, cycle and organ. Descriptive statistics, including geometric mean and geometric Coefficient of Variation (CV), will be presented by study part, cohort (part B only) and cycle on the PP-DAS.

Uptake (unit: %) in discernible organs at each assessment time point will be also displayed, it will be listed by study part, cohort (part B only), radioactivity level adapted or not (part B only), subject, cycle, organ and time point, along with dosimetry parameters. Descriptive statistics, including geometric mean and geometric Coefficient of Variation (CV), will be presented by study part, cohort (part B only), cycle and time point on the PP-DAS. A linear plot of the mean of the uptake (%) in discernible organs over time will be displayed by study part, cohort (part B only), radioactivity level adapted or not (part B only) and cycle on PP-DAS.

- Areas Under the Curve (AUCs) of ^{177}Lu -OPS201 in discernible thoracic and abdominal organs (unit: MBq*h), lesions (unit: MBq*h) and blood (unit: MBq/L*h).

AUCs of ^{177}Lu -OPS201 in discernible thoracic and abdominal organs (unit: h*MBq) will be listed by study part, cohort (part B only), radioactivity level adapted or not (part B only), subject, cycle and organ. Descriptive statistics, including geometric mean and geometric Coefficient of Variation (CV), will be presented by study part, cohort (part B only), cycle, organ on the PP-DAS.

AUCs of ^{177}Lu -OPS201 in lesions (unit: h*MBq) will be listed by study part, cohort (part B only), radioactivity level adapted or not (part B only), subject, cycle and lesion number.

AUCs of ^{177}Lu -OPS201 in blood (unit: MBq/L*h) will be listed by study part, cohort (part B only), radioactivity level adapted or not (part B only), subject and cycle. Descriptive statistics, including geometric mean and geometric Coefficient of Variation (CV), will be presented by study part, cohort (part B only) and cycle on the Radiopharmaceutical Pharmacokinetic Set.

- Uptake in blood (unit: %/L)

At each assessment time point will also displayed, it will be listed by study part, cohort (part B only), radioactivity level adapted or not (part B only), subject, cycle and time point. Descriptive statistics, including geometric mean and geometric Coefficient of Variation (CV), will be presented by study part, cohort (part B only), cycle and time point on the Radiopharmaceutical Pharmacokinetic Set. Graphs of the mean of the uptake in blood (unit: %/L) over time will be displayed by study part, cohort (part B only), radioactivity level adapted or not (part B only) and cycle on the Radiopharmaceutical Pharmacokinetic Set.

- Terminal half-life of radioactivity concentrations of the radiopharmaceutical in blood (unit: h).

Terminal half-life of radioactivity concentrations in blood (unit: h) will be listed by study part, cohort (part B only), radioactivity level adapted or not (part B only), subject and cycle. Descriptive statistics, including geometric mean and geometric Coefficient of Variation (CV), will be presented by study part, cohort (part B only), radioactivity level adapted or not (part B only) and cycle on the Radiopharmaceutical Pharmacokinetic Set.

- Cumulatively excreted radioactivity in urine (unit: MBq) in each time period, 0 - 6 hours, 6 - 24 hours and 24 - 48 hours and overall on the 0-48 hours period (if there is no missing collection period).

Cumulatively excreted radioactivity in urine (unit: MBq) will be listed by study part, cohort (part B only), radioactivity level adapted or not (part B only), subject, cycle and time period.

Descriptive statistics, including geometric mean and geometric Coefficient of Variation (CV), will be presented by study part, cohort (part B only), cycle and time period on the ITT Set.

(b) Radiation Dosimetry

- Organs receiving the highest absorbed dose (unit: Gy).

All organs with their absorbed dose will be listed by study part, cohort (part B only), radioactivity level adapted or not (part B only), cycle, organ and subject on the ITT- DAS, and highest dose will be flagged.

- Specific absorbed dose to the lesions selected for the dosimetry evaluation (unit: Gy/GBq).

Specific absorbed dose to the lesions selected for the dosimetry evaluation will be listed by study part, cohort (part B only), radioactivity level adapted or not (part B only), subject, cycle and lesion number. Descriptive statistics, including geometric mean and geometric Coefficient of Variation (CV), will be presented by study part, cohort (part B only), cycle and lesion location on the ITT- DAS and PP-DAS. Descriptive statistics will also be presented on combined lesions on the PP-DAS population.

- Specific absorbed dose per organ (unit: Gy/GBq).

Specific absorbed dose per organ will be listed by study part, cohort (part B only), radioactivity level adapted or not (part B only), subject, cycle and organ. Descriptive statistics, including geometric mean and geometric Coefficient of Variation (CV), will be presented by study part, cohort (part B only), cycle and organ on the ITT- DAS and PP-DAS.

- Ratio of Specific absorbed dose per organ and lesion.

Ratio of specific absorbed dose at visits (e.g. visit 2 relative to visit 1, visit 3 relative to visit 1, visit 2 relative to visit 3, etc..) will be calculated per organ and per lesion and by study part (Part A and B), and by each cohort (applies to part B only), radioactivity level adapted or not (applies to part B only), subject, cycle and organ. Descriptive statistics, including geometric mean and geometric Coefficient of Variation (CV), will be presented by study part, cohort (part B only), cycle and organ on the PP-DAS.

Boxplots representing the ratio of specific absorbed doses between visits by organ and lesion will be produced.

- Tumour average/kidney ratio

Ratio of tumour/average kidney ratio between visits by organ or combined lesions will be calculated per lesion and by study part (Part A and B), and by each cohort (applies to part B only), radioactivity level adapted or not (applies to part B only), subject and cycle.

Descriptive statistics, including geometric mean and geometric Coefficient of Variation (CV), will be presented by study part, cohort (part B only), cycle and organ on the PP-DAS.

- Cumulative absorbed organ doses (unit: Gy)

Cumulative absorbed organ doses will be listed by study part, cohort (part B only), radioactivity level adapted or not (part B only), organ and subject.

Descriptive statistics, including geometric mean and geometric Coefficient of Variation (CV), will be presented by study part, cohort (part B only) and organ on the ITT- DAS and PP-DAS.

CCI

(d) OPS201 Pharmacokinetics (Part B only)

Analysis of PK data by non-compartmental approach will be documented in a separate analysis plan. A listing of PK sampling time deviation from the scheduled time will be provided on OPS201 PK population. A listing of individual OPS201 concentrations per time point will be provided on OPS201 PK population.

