9.1 Pharmacokinetics of the Radiopharmaceutical

9.1.1 *Blood Sample Collection*

For each subject, total radioactivity concentration in whole blood will be measured. Each subject will have blood samples (2 mL) taken as follows:

Visit 1:

- Before infusion, at stop of infusion (0), 5 minutes \pm 1 minute, 30 minutes \pm 3 minutes, 1 hour \pm 5 minutes, 4 hours \pm 10 minutes, 24 \pm 1 hours, 48 \pm 1 hours, 72 to 96 hours, and 144 to 168 hours after the stop of infusion.

Visits 2 and 3:

- Before infusion, at stop of infusion (0), 1 hour \pm 5 minutes, 4 hours \pm 10 minutes, 24 \pm 1 hour, 48 \pm 1 hour, 72 to 96 hours and 144 to 168 hours.

For subjects receiving additional administrations (up to two additional cycles, Part B only), blood samples will be taken at each cycle according to the timepoints described above for Visits 2 and 3.

Blood samples should be collected from the contralateral arm used for the study drug infusion, or from another anatomical site.

The accurate time of sample collection and the duration for measuring the radioactivity concentration must be recorded. Any issues associated with sample collection or processing should be reported to the sponsor's monitor.

Complete instructions for sample collection, processing and handling will be provided in a "Dosimetry Operation Manual".

9.1.2 *Urine Sample Collection*

To determine the renal excretion of ^{177}Lu , urine will be collected during the first 48 hours post infusion at the following time periods:

Visit 1 only:

- **Part A:** from the start of the infusion to 6 hours, 6 to 24 hours, 24 to 48 hours postinfusion
- **Part B:** from the start of the infusion to 4 hours, 4 to 24 hours, 24 to 48 hours (from the start of the infusion to 4 hours postinfusion only for US and Canada sites)

The accurate time of urine collection and the total urine volume for each collection interval must be recorded. All problems associated with sample collection or processing should be reported to the sponsor's monitor.

Complete instructions for urine collection, processing and handling will be provided in a "Dosimetry Operation Manual".

9.1.3 *Analytical Procedures*

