11.4 Statistical/Analytical Methods

Statistical analyses will be performed by external contract research organisations (CROs), managed by the sponsor’s Biometry Department.

Details of the statistical analysis are specified in the SAP.

The statistical analyses will be conducted using SAS (v9.2 or later).

Primarily, all variables will be analysed descriptively, as follows:

- Mean, standard deviation, median and range for continuous variables
- Median, range and frequency distribution for discrete (ordinal) variables
- Frequency distribution for nominal variables.

Secondarily, the variables descriptive statistics will be presented by study part. If appropriate, results for total, Part A+B will be presented. In the event of dose escalation, study Parts A and B will be compared using nonparametric tests. The test results will be interpreted in an exploratory manner. 95% confidence intervals will be estimated as appropriate.

Data collected during the Long-term Follow-up will be analysed by means of a survival analysis (Kaplan-Meier method) with the respective plots and descriptive summaries.

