(d) Terminal half-life of radioactivity concentrations in blood (unit: h).

The terminal half-life is defined as the lowest decay rate of the AUC fit performed for blood (Ref. 11).

- (e) Other biodistribution and radioactive pharmacokinetics of the radiopharmaceutical variables

Cumulatively excreted activity in urine (unit: MBq) in each time period, 0 to 6 hours and 6 to 24 hours post-infusion (Part A), and 0 to 4 hours, 4 to 24 hours, 24 to 48 hours (Part B).

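### Organ AUC, blood AUC and urinary excretion are summarised without dividing by injected activity, and SAP 3.2.2 names urine intervals that Part B does not collect

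*SAP*

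**What the plan says.** **Units.** SAP 3.1.2.1(c) and 3.2.2(a) define AUC in activity units. Organ AUC "in discernible thoracic and abdominal organs (unit: h*MBq) will be listed by study part" and blood AUC "in blood (unit: MBq/L*h) will be listed by study part, cohort (part B only" also receive descriptive statistics, including geometric mean and CV, by part, cohort and cycle. Lesion AUC "in lesions (unit: h*MBq) will be listed by study part", and no statistics follow. Urinary excretion is in MBq, with descriptive statistics by part, cohort, cycle and period. The opening of SAP 3.2.2 adds pooled rows: "Summary tables will be presented by study part, cohort (part B only), overall part B and overall". Protocol 11.4 says that, if the dose is escalated, "study Parts A and B will be compared using nonparametric tests", to be read as exploratory.

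**Urine intervals.** SAP 3.2.2 reports urine "in each time period, 0 - 6 hours, 6 - 24 hours and 24 - 48 hours", plus a 0-48 h total when no period is missing. It does not distinguish the parts. Protocol 11.4.7 names the same three intervals for each subject. Protocol 9.1.2 has Part B collecting urine "from the start of the infusion to 4 hours, 4 to 24 hours, 24 to 48 hours", with only the first interval at US and Canada sites. Part A collects to 6 h, 6-24 h and 24-48 h. SAP 3.1.2.1(e) gives "0 to 6 hours and 6 to 24 hours post-infusion (Part A", with no 24-48 h period for that part, and then lists the Part B intervals as collected.

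**The concern.** If two subjects handle the product identically and one receives more activity, that subject's AUC in MBq*h and urine in MBq are larger in the same proportion. The planned activity per cycle differs by cohort, varies by ±10% around each target, and can be lowered for an individual's later cycles. A between-cohort or pooled table in raw units therefore mixes the amount given with the way the body handled it. A larger AUC at a higher activity could be taken for altered kinetics, and a pooled CV would contain spread that the design put there.

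The urine intervals raise a different problem. A programmer following SAP 3.2.2 would set up 0-6 h and 6-24 h rows that no Part B subject can fill. One following SAP 3.1.2.1(e) would drop a Part A period that was collected.

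**Working it through.** **Inputs.** Activity per cycle from SAP Table 1 and Protocol Table 11: 4.5 GBq (Cohorts 3 and 6; Part A is also 4.5), 6.0 GBq (Cohorts 1, 4, 7) and 7.4 GBq (Cohorts 2, 5, 8), each ±10%. Planned maximum enrolment from Protocol 3.1.3: Cohort 1 has 5, Cohorts 3 and 6 have 10 each, and the other five have 3 each, 40 in total.

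**The plan's own totals.** 3 × 4.5 = 13.5, 3 × 6.0 = 18.0 and 3 × 7.4 = 22.2 GBq. All match SAP Table 1.

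**Between activity levels.** With identical kinetics, raw AUC = k × injected activity with k constant, so the ratio of raw values equals the ratio of activities:
- 6.0/4.5 = 1.33
- 7.4/4.5 = 1.64
- 7.4/6.0 = 1.23

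Dividing by injected activity returns 1.00 in each case.

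**Within one activity level.** Two administrations at opposite tolerance limits differ by at most 1.1/0.9 = 1.22, before any individual reduction.

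**Pooled Part B against Part A.** At maximum enrolment, 20 subjects are at 4.5, 11 at 6.0 and 9 at 7.4 GBq.
- Geometric mean = exp[(20 ln 4.5 + 11 ln 6.0 + 9 ln 7.4)/40] = exp(1.6951) = 5.45 GBq, and 5.45/4.5 = 1.21.
- Variance of ln activity (divisor 39) = 0.0430. Geometric CV = √(exp(0.0430) − 1) = 0.21, so about 21% arises from activity alone.
- If optional Cohorts 2, 7 and 8 are not opened and the other numbers are unchanged (20, 8 and 3 subjects): exp[(20 ln 4.5 + 8 ln 6.0 + 3 ln 7.4)/31] = 5.09 GBq, and 5.09/4.5 = 1.13.

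**Which quantities already have a normalised summary (SAP 3.1.2.1, 3.1.3, 3.2.2).**
- Organs: uptake as % of injected activity, and specific absorbed dose in Gy/GBq.
- Blood: % of injected activity per litre at each time point, and terminal half-life. Integrated exposure per injected activity has none.
- Urine: none.

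**Urine intervals side by side.**

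| Source | Part A | Part B |
|---|---|---|
| Collected (Protocol 9.1.2) | 0-6, 6-24, 24-48 h | 0-4, 4-24, 24-48 h; US and Canada 0-4 h only |
| SAP 3.1.2.1(e) | 0-6, 6-24 h | 0-4, 4-24, 24-48 h |
| SAP 3.2.2 | 0-6, 6-24, 24-48 h | the same, parts not separated |
| Protocol 11.4.7 | 0-6, 6-24, 24-48 h | the same, parts not separated |

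The windows that both parts can supply are 0-24 h (0-6 plus 6-24 against 0-4 plus 4-24), 24-48 h and 0-48 h. US and Canada Part B subjects can supply none of the three.

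**The case against.** The strongest reply is that the kinetic information is already in the tables. Blood uptake in % of injected activity per litre is summarised and plotted by part, cohort and cycle, on the same analysis set as blood AUC. Half-life does not depend on activity, and organs have both % uptake and Gy/GBq. This largely stands. For blood, however, summaries at separate time points do not give the centre and spread of each subject's integrated exposure, and urine has no normalised summary at all.

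A reader might also infer that the peptide-mass question is confounded with activity. The design does not support that. Mass is changed within subject at 4.5 GBq in Cohorts 3 and 6, and between cohorts at fixed nominal activity in 1/4/7 and 2/5/8. Part A shares 4.5 GBq with Cohorts 3 and 6. Only the tolerance and individual reductions remain there, and the AUC listings flag whether activity was adapted. Reductions in later cycles cannot affect urine, which is collected at Visit 1 only.

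A 2.0-fold distortion is another tempting figure: (7.4 × 1.1)/(4.5 × 0.9) = 2.01. It compares two single administrations at opposite tolerance limits, not cohort averages.

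Nor is it true that none of the stated urine intervals exists in Part B. The 24-48 h period is collected outside the US and Canada, and SAP 3.1.2.1(e) has the correct Part B set. This is an internal contradiction, not a choice of analysis.

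Finally, the Part A versus Part B test in Protocol 11.4 is general, conditional and exploratory. SAP 3.1.9 plans no formal testing, and the AUC and urine text names no test.

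**Conclusion.** The point holds in a limited form. Organ AUC, blood AUC and urinary excretion are summarised in units that carry the administered activity. At nominal activity and with identical kinetics, this produces differences of 1.33-fold (6.0 against 4.5 GBq) and 1.64-fold (7.4 against 4.5 GBq). Pooled Part B would exceed Part A by about 1.21-fold at planned maximum enrolment, or about 1.13-fold without the optional cohorts. The rows affected are comparisons across activity levels and the pooled Part B and overall rows. Lesion AUC is outside the point because it is only listed.

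The material gap is the lack of any normalised summary of integrated blood exposure and of urine. Separately, the 0-6 h and 6-24 h rows cannot be produced for any Part B subject, up to 40 of the planned 55, and the SAP disagrees with itself on the intervals.

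The ratios assume proportionality to injected activity and nominal doses. The shared urine windows assume that both parts count from the same origin, which Protocol 9.1.2 gives as the start of infusion. These are secondary descriptive outputs: neither the primary safety endpoint nor the written escalation rules use AUC or urinary MBq. The change should still be made because it is cheap and removes a predictable misreading.

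**What to change.** - In SAP 3.1.2.1(c) and (e) and 3.2.2(a), add AUC divided by the injected activity of that cycle (h for organs, h/L for blood) and urine as % of injected activity. Use these for the by-part, pooled and between-cohort summaries. Raw MBq values may be kept alongside.
- In SAP 3.2.2 and Protocol 11.4.7, state the urine intervals by part as collected: 0-6, 6-24 and 24-48 h in Part A; 0-4, 4-24 and 24-48 h in Part B. Add 24-48 h for Part A in SAP 3.1.2.1(e).
- Compare urine between parts only over 0-24, 24-48 and 0-48 h. Report US and Canada Part B subjects for 0-4 h only, and say that periods never scheduled for them do not yield a 0-48 h total.

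The cost is wording and one division per record. The SAP already uses the actual injected activity to calculate % uptake, so no new data are needed.
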